Appendix B. Schedule of Events

Test or Procedure	Visit 1 -2 Week Screening	Visit 2 Week 0	Visit 3 Week 1 ± 2 days	Visit 4 Week 4 ± 3 days	Visit 5 Week 8 ± 3 days	Visit 6 Week 12 ± 3 days	Visit 7 Week 24 ± 3 days
Informed Consent Process	X						
Inclusion and Exclusion Criteria	X						
Demography	X						
Medical History	X	X ⁵	X	X	X	X	X
Physical Examination	X	X ⁵	X	X	X	X	X
Physical Examination of Penis ¹	X	X ⁵	X	X	X	X	X
Vital Signs	X	X	X	X	X	X	X
Blood Tests (Chemistry and Hematology) ²	X ⁴		X	X		X	X
Urine analysis ³	X	X ⁵	X	X		X	X
ECG ⁴	X	X ⁴	X	X	X	X	X
IIEF ⁵	X	X ⁵	X	X	X	X	X
SEP ⁵		X ⁵	X	X	X	X	X
Study drug administration		X					
Concomitant Medications	X	X	X	X	X	X	X
Adverse Events		X	X	X	X	X	X
Assay for hSlo DNA ⁶	X ⁶	X	X	X	X	X	X

¹PE of penis includes: inspection, palpation and neurosensory testing

²Blood tests include: Hematology (CBC with differential, platelet count, PTT, PT, sedimentation rate, CRP), Chemistry (BUN, Cr, Na⁺, K⁺, Mg⁺⁺, Ca⁺⁺, CO₂, Cl, albumin, alkaline phosphatase, ALT, AST, total bilirubin, total protein; Endocrine (testosterone, random cortisol, TSH, T4). Hemoglobin A1c at Screening (V1) only.

³Urine analysis includes: microscopic RBC and WBC, protein, glucose, and specific gravity.

⁴ECG at V2 will be done prior to administration of study drug and at 1 and 2 hours following administration of study drug

⁵Test will be done prior to administration of study drug.

⁶In all participants, plasma specimens will be collected to assay for the presence of hSlo DNA by PCR. At Visit 2 collect pre- dosing and 2 post dosing.

Appendix C. Sexual Encounter Profile (SEP)

Sexual Encounter Profile DIARY

Questions to be addressed after each attempt at intercourse	____/____/____ MM/DD/YY	____/____/____ MM/DD/YY	____/____/____ MM/DD/YY	____/____/____ MM/DD/YY
1. Were you able to achieve at least some erection?	N Y	N Y	N Y	N Y
2. Were you able to insert your penis into your partner's vagina?	N Y	N Y	N Y	N Y
3. Did your erection last long enough for you to have successful intercourse?	N Y	N Y	N Y	N Y
4. Were you satisfied with the hardness of your erection?	N Y	N Y	N Y	N Y
5. Overall, were you satisfied with the sexual experience?	N Y	N Y	N Y	N Y

Appendix D. International Index Erectile Function

INTERNATIONAL INDEX OF ERECTILE FUNCTION PAGE 1 OF 2

PARTICIPANT

(check the appropriate box – *In the last month.....*)

1. How often were you able to get an erection during sexual activity?	4. During sexual intercourse, how often were you able to maintain your erection after you had penetrated (entered) your partner?
0. No sexual activity..... 	0. Did not attempt intercourse..... 
1. Almost never / never..... 	1. Almost never / never..... 
2. A few times (much less than half the time)..... 	2. A few times (much less than half the time)..... 
3. Sometimes (about half the time)..... 	3. Sometimes (about half the time)..... 
4. Most times (much more than half the time)..... 	4. Most times (much more than half the time)..... 
5. Almost always/always..... 	5. Almost always/always..... 
2. When you had erections with sexual simulation, how often were your erections hard enough for penetration?	5. During sexual intercourse, how difficult was it to maintain your erection to completion of intercourse?
0. No sexual activity..... 	0. Did not attempt intercourse..... 
1. Almost never / never..... 	1. Extremely difficult..... 
2. A few times (much less than half the time)..... 	2. Very difficult..... 
3. Sometimes (about half the time)..... 	3. Difficult..... 
4. Most times (much more than half the time)..... 	4. Slightly difficult..... 
5. Almost always/always..... 	5. Not difficult..... 
3. When you attempted sexual intercourse, how often were you able to penetrate (enter) your partner?	6. How many times have you attempted sexual intercourse?
0. No sexual activity..... 	0. No attempts..... 
1. Almost never / never..... 	1. One to two times..... 
2. A few times (much less than half the time)..... 	2. Three to four times..... 
3. Sometimes (about half the time)..... 	3. Five to six times..... 
4. Most times (much more than half the time)..... 	4. Seven to ten times..... 
5. Almost always/always..... 	5. Eleven + times..... 
7. When you attempted sexual intercourse, how often was it satisfying for you?	
	0. Did not attempt intercourse..... 
	1. Almost never / never..... 
	2. A few times (much less than half the time)..... 
	3. Sometimes (about half the time)..... 
	4. Most times (much more than half the time)..... 
	5. Almost always/always..... 

INTERNATIONAL INDEX OF ERECTILE FUNCTION PAGE 2 OF 2


8. How much have you enjoyed sexual intercourse?
 
0. No intercourse..... 1. No enjoyment..... 2. Not very enjoyable..... 3. Fairly enjoyable..... 4. Highly enjoyable..... 5. Very enjoyable.....
 
9. When you had sexual stimulation or intercourse, how often did you ejaculate?
 
0. No sexual stimulation/intercourse  1. Almost never/never..... 2. A few time (much less than half the time)..... 3. Sometimes(about half the time).... 4. Most times (much more than half the time)..... 5. Almost always/always.....
 
10. When you had sexual stimulation or intercourse, how often did you have the feeling or orgasm or climax?
 
0. No sexual stimulation/intercourse..... 1. Almost never/never..... 2. A few time (much less than half the time)..... 3. Sometimes(about half the time).... 4. Most times (much more than half the time)..... 5. Almost always/always.....
 
11. How often have you felt sexual desire?
 
1. Almost never/never..... 2. A few times (much less than half the time)..... 3. Sometimes (about half the time). 4. Most times (much more than half the time)..... 5. Almost always/always.....
	
12. How would you rate your level of sexual desire?
 
1. Very low/none at all..... 2. Low..... 3. Moderate..... 4. High..... 5. Very high.....
 
13. How satisfied have you been with your overall sex life?
 
1. Very dissatisfied..... 2. Moderately dissatisfied..... 3. About equally satisfied and dissatisfied..... 4. Moderately satisfied..... 5. Very satisfied.....
 
14. How satisfied have you been with your sexual relationship with your partner?
 
1. Very dissatisfied..... 2. Moderately dissatisfied..... 3. About equally satisfied and dissatisfied..... 4. Moderately satisfied..... 5. Very satisfied.....
 
15. How do you rate your confidence that you could get and keep an erection?
 
1. Very low..... 2. Low..... 3. Moderate..... 4. High..... 5. Very high.....

---	---

## STATISTICAL ANALYSIS PLAN

ION04ED

### 2. List of Abbreviations

Term	Definition
AE	Adverse event
DLT	Dose Limiting Toxicities
ED	Erectile Dysfunction
EF	Erectile Function
ECG	Electrocardiogram
BUN	Blood Urea Nitrogen
CBC	Complete Blood Count
CRF	Case Report Form
IIEF	International Index of Erectile Function
IU	International Unit
IC	Intracavernous
ITT	Intent-to-treat
Mod-ITT	Modified Intent-to-treat
PP	Per protocol
PT	Prothrombin Time
PTT	Partial Thromboplastin
SEP	Sexual Encounter Profile
SEP2	Ability to achieve vaginal penetration
SEP3	Ability to maintain an erection long enough for successful intercourse
Sed. rate	sedimentation rate
VED	Vacuum Erection Devices

### 3. Introduction

Erectile Dysfunction (ED) is a disease defined as the inability to achieve or maintain an erection sufficient for satisfactory sexual function. The most common cause of ED is advanced age. Proposed causes of age-induced ED include reduction of NO production, increased contractility of the smooth muscle of the penile corpora, increased myofilament calcium sensitivity due to altered *Rho* kinase expression/activity, and reduction in the relative percentage of smooth muscle fibers and an increase in collagen content thus decreasing the compliance of the cavernous tissue. The second most common cause is diminished blood flow to the penis due to cardiovascular disease.

ED can either be reversible or nonreversible. Men over 50 years tend to have permanent causes of ED that are disease-related. The most frequently associated diseases include atherosclerosis, hypertension, anti-hypertensive medications, diabetes mellitus, and pelvic surgery and radiation. In younger men (ages 20 – 40), psychological causes for ED often predominate and this reversible form of ED can be treated with sex therapy and drugs.

Ion Channel Innovations has developed *hMaxi-K* to treat ED using the same principal as drugs that have been used since 1982, i.e., treatment with medicines causing relaxation of the penile smooth muscle resulting in rigid erections. *hMaxi-K* consists of the gene for the  $\alpha$ -pore subunit of the maxi-K channel, *hSlo*, inserted into a plasmid vector. Administration of this gene into the corpora increases expression of the maxi-K channel in the smooth muscle cells and an increased efflux of  $K^+$  across the cell membrane resulting in decreased entry of  $Ca^{++}$  ions. This effect on ion exchange across the smooth muscle cells allows the smooth muscle of the corpora to relax; the corporal sinusoids become engorged with blood, and the penis to stay rigid. Furthermore, results from these preclinical studies suggest that expression of the  $\alpha$ -pore subunit for the maxi-K channel following administration of *hMaxi-K* may have a long-term effect on the erectile mechanism. This activity of *hMaxi-K* may represent a distinct advantage over current drug therapy for ED where the effect of treatment is temporary.

This statistical analysis plan describes in detail the methods and presentation of the data analyses for the study ION04-ED to evaluate the safety and efficacy of a single intracavernous injection of *hMaxi K* (8000  $\mu$ g and 16000  $\mu$ g) or placebo upon penile rigidity or erection in males with erectile dysfunction longer than six months that is attributable to an underlying, stable medical condition.

This study is double-blind, placebo controlled parallel design Phase 2A trial evaluating the potential activity and safety of two different doses of *hMaxi-K* (16000  $\mu$ g, and 8000 $\mu$ g) given in a single administration relative to placebo injected into the corpus cavernosum of the penis. The proposed study period is approximately 6 months following the single injection of study drug per participant. This study will enroll 11 participants at *hMaxi-K* doses of 8000  $\mu$ g, 11 participants at *hMaxi-K* doses of 16000  $\mu$ g and 13 on placebo. A maximum of 35 participants will be enrolled.

## STATISTICAL ANALYSIS PLAN

### ION04ED

#### Schedule of Events

Test or Procedure	Visit 1 -2 Week Screening	Visit 2 Week 0	Visit 3 Week 1 ± 2 days	Visit 4 Week 4 ± 3 days	Visit 5 Week 8 ± 3 days	Visit 6 Week 12 ± 3 days	Visit 7 Week 24 ± 3 days
Informed Consent Process	X						
Medical History	X	X 	X	X	X	X	X
Physical Examination	X	X 	X	X	X	X	X
Physical Examination of Penis 	X	X 	X	X	X	X	X
Blood Tests (Chemistry and Hematology) 	X 		X	X		X	X
Urine analysis 	X	X 	X	X		X	X
ECG 	X	X 	X	X	X	X	X
IIEF 	X	X 	X	X	X	X	X
SEP 		X 	X	X	X	X	X
Study drug administration		X					
Assay for h Slo DNA 	X 	X	X	X	X	X	X

PE of penis includes: inspection, palpation and neurosensory testing

Blood tests include: Hematology (CBC with differential, platelet count, PTT, PT, sedimentation rate, CRP), Chemistry (BUN, Cr, Na+, K+, Mg++, Ca++, CO2, Cl, albumin, alkaline phosphatase, ALT, AST, total bilirubin, total protein; Endocrine (testosterone, random cortisol, TSH, T4). Hemoglobin A1c and prolactin at Screening (V1) only.

Urine analysis includes: microscopic RBC and WBC, protein, glucose, and specific gravity.

ECG at V2 will be done prior to administration of study drug and at 1 and 2 hours following administration of study drug

Test will be done prior to administration of study drug.

In all participants, plasma specimens will be collected to assay for the presence of *h*Slo DNA by PCR. At Visit 2 collect pre- dosing and 2 post dosing.

#### 4. Study Objective

The objective of the study is to evaluate the safety and efficacy of a single intracavernous injection of *h*Maxi K (8000 µg and 16000 µg) or placebo upon penile rigidity or erection in males with erectile dysfunction longer than six months that is attributable to an underlying, stable medical condition.

##### Primary objective

The primary objective of this study is to evaluate the potential efficacy and safety of a single intracavernous injection of *h*Maxi-K (16,000 µg) compared to placebo in males with erectile dysfunction longer than six months that was attributable to an underlying, stable medical condition upon penile rigidity or erection in males with erectile dysfunction longer than six months that is attributable to underlying, stable medical condition.

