11.1 Informed Consent	30
12.0 Regulatory Standards.....	30
12.1 Electronic case report forms	30
12.2 Clinical and Regulatory Monitoring.....	30
12.2.1 Study Conduct (Site)	30
12.2.2 Adherence to Reporting Requirements	31
12.3 Participant Confidentiality	31
12.4 Records.....	32
13.0 References	32
Appendix A. Grading of Averse Events	36
Appendix B. Schedule of Events.....	38
Appendix C. Sexual Encounter Profile (SEP).....	39
Appendix D. International Index Erectile Function.....	40

List of Figures

Figure 1: Regulation of Myocyte Tone.....	8
Figure 2. Interaction of Maxi-K channel and nitric oxide. See text for explanation.....	10

List of Tables

Table 1. - Final Dose – h Maxi-K	16
Table 2. Statistical Power	29

Protocol Synopsis

Title	A Double-blind, Placebo-controlled, Parallel Design, Randomized Phase 2A Trial Evaluating the Potential Activity and Safety of hMaxi-K Gene Transfer in Males with Erectile Dysfunction
Study Number	ION 04-ED
Clinical Study Phase	Phase 2A
Number of Centers	One site
Study Objectives	To evaluate the safety and efficacy of a single intracavernous injection of hMaxi K (8000 µg and 16000 µg) or placebo upon penile rigidity or erection in males with erectile dysfunction longer than six months that is attributable to an underlying, stable medical condition.
Study Design	This study is a double-blind, placebo controlled, parallel design, Phase 2A study evaluating the potential activity and safety of a single administration of hMaxi-K (8000 or 16000 µg) or placebo (PBS sucrose 20%) injected into the corpus cavernosum of the penis in men who have been unable to tolerate, do not wish to continue, or have had unsuccessful results with, prior therapy for ED.
Study Participant Population	The study population is men with erectile dysfunction attributable to an underlying, stable medical condition but who are otherwise in good health. The target population is men with erectile dysfunction and those who have been unable to tolerate, do not wish to continue, or have had unsuccessful results with, prior therapy for ED and with an erectile function domain score of IIEF >10 and < 21 at screening and baseline.

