Study Procedures	Following screening and study drug administration at week 0, eligible participants will be evaluated at weeks 1, 4, 8, 12, and 24. At each study visit, participants will have a physical examination including examination of the penis (all visits), vital signs, electrocardiogram (ECG) (all visits). Laboratory evaluations including chemistry and hematology will be done at V1, 3, 4, 6, and 7. Urinalysis will be done V1, 2 (prior to dosing), 3, 4, 6, and 7. Endocrine parameters and PTT, PT, sed rate and CRP will be evaluated at Visit 1, 3 and 7. The participant will complete the erectile function domain of the IIEF and Sexual Encounter Profile (SEP) at screening/baseline and at V2, (SEP and IIEF at V2 prior to dosing) V3, V4, V5, V6, and V7. In all participants, plasma specimens will be collected to assay for the presence of hSlo DNA by PCR (V2-V7). These will be kept frozen at -20°C or less at the site for eventual assay by Sponsor.
Primary Study Outcomes	The primary outcome measures will include the Erectile Function (EF) domain of the International Index of Erectile Function (IIEF), Sexual Encounter Profile (SEP), Questions 2 and 3 from SEP. The IIEF EF domain has a 30-point total score, where higher scores reflect better erectile function. SEP is a diary in which participants record each sexual attempt made throughout the study. The two questions from the Sexual Encounter Profile (SEP) deal with the ability to achieve vaginal penetration (SEP2), and the ability to maintain an erection long enough for successful intercourse (SEP3). The erectile function domain category of the IIEF will be used to evaluate the change in erectile status from baseline following

**Secondary
Study
Outcome****Study Duration****Study Start****Sample Size****Statistical
Analysis**

administration of *h*Maxi-K. Change from baseline on the six questions of the IIEF's Erectile function domain category at every visit after administration of study drug will be calculated and compared among the two dose and one placebo groups.

Safety will be assessed by analysis of adverse experiences, and abnormal findings on clinical laboratory tests, electrocardiogram, and physical examinations.

6 months per participant (approximately 1 year to enroll all participants)

TBD

35 participants; N=11 on 8000 µg; N= 11 on 16000 µg; N= 13 on placebo

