1.6 Clinical Data

2.0 Objectives

The primary objective of this study is to evaluate the safety of a single intracavernous injection of *h*Maxi-K (either 8,000 or 16,000 µg) compared to placebo in males with erectile dysfunction longer than six months that was attributable to an underlying, stable medical condition upon penile rigidity or erection in males with erectile dysfunction longer than six months that is attributable to underlying, stable medical condition.

The secondary objective of this study is to evaluate the efficacy of a single intracavernous injection of *h*Maxi-K, either 8,000 or 16,000 µg, compared to placebo.

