##### Secondary objective

The secondary objective of this study is to evaluate safety of a single intracavernous injection of *h*Maxi-K, either 8,000 or 16,000 µg, compared to placebo.

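### Protocol and SAP rank safety and efficacy differently and name different primary doses, and the alpha plan fits neither ranking.

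*SAP*

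**What the plan says.** **Protocol, Section 2.0.** Primary: "The primary objective of this study is to evaluate the safety of a single intracavernous injection of" hMaxi-K, at 8,000 or 16,000 µg, against placebo. Secondary: "The secondary objective of this study is to evaluate the efficacy of a single intracavernous injection of" hMaxi-K, "either 8,000 or 16,000" µg, against placebo.

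**Protocol synopsis.** The objective is "To evaluate the safety and efficacy of a single intracavernous injection of" hMaxi-K at both doses, with no ranking. The outcomes are ranked: "The primary outcome measures will include the Erectile Function (EF) domain of the International Index of Erectile Function (IIEF"), together with SEP questions 2 and 3. Safety ("Safety will be assessed by analysis of adverse experiences, and abnormal findings on clinical laboratory tests" and other examinations) appears to belong under the secondary-outcome heading, but the synopsis table is broken in the text available, so that placement is an inference.

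**SAP, Section 4.** A general objective covers safety and efficacy of both doses, unranked. Two ranked objectives follow. Primary: "The primary objective of this study is to evaluate the potential efficacy and safety of a single intracavernous injection of" hMaxi-K, at 16,000 µg only. Secondary: "The secondary objective of this study is to evaluate safety of a single intracavernous injection of" hMaxi-K, at 8,000 or 16,000 µg. The primary outcome measures, here and in Section 9.3, are the IIEF erectile function domain and SEP2/SEP3.

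**Sample size (Protocol 10.3.2, SAP Section 8).** One calculation, on means of 10.0 v 6.6 with SD 2.5, groups of 11, 11 and 13, and an adjusted alpha of 0.0167 for three comparisons. The protocol lists dose v dose and each dose v placebo. The SAP adds pooled active v placebo but still counts three.

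**The concern.** A reader cannot tell from the ranked objectives whether the trial stands or falls on safety or on efficacy, or whether the primary efficacy question concerns one dose or two. That matters in three ways.

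- If Protocol 2.0 governs, the primary objective has no hypothesis or power behind it, since safety is only tabulated and summarised.
- If SAP Section 4 governs, one dose carries the primary efficacy question, yet alpha is divided as if the dose contrasts were equal members of one family.
- Both documents claim that overall alpha is held at 0.05. That claim needs a defined primary family, and the objectives do not supply one consistently.

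A primary contrast chosen after the code is broken could be driven by the data.

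**Working it through.** **Step 1. The texts side by side.**

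| Source | Primary | Secondary |
|---|---|---|
| Protocol 2.0 | Safety, either dose | Efficacy, either dose |
| Synopsis objective | Safety and efficacy, both doses, unranked | None stated |
| Synopsis outcomes | IIEF-EF, SEP2, SEP3 | Safety (inferred) |
| SAP 4, general objective | Safety and efficacy, both doses, unranked | None stated |
| SAP 4, ranked objectives | Efficacy and safety, 16,000 µg | Safety, either dose |
| SAP 4 and 9.3, outcomes | IIEF-EF, SEP2, SEP3 | Not ranked |

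Three things follow.

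- The two ranked sets of objectives (Protocol 2.0 and SAP 4) disagree on the place of efficacy and on the primary dose.
- Within the SAP, safety of 16,000 µg is both primary and secondary.
- Efficacy of 8,000 µg is a protocol secondary objective but is in neither ranked SAP objective. It is covered by the SAP's unranked general objective and by the repeat analyses in Section 9.3.

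**Step 2. What the sample size was built for.** Inputs from Protocol Table 2 and SAP Section 8: difference 10.0 − 6.6 = 3.4; SD 2.5; alpha 0.05/3 = 0.0167; power 80%; ratio 1.111.

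- One-sided t-test: the smallest n giving 80% at this ratio is 11, with 1.111 × 11 = 12.2, rounded up to 13.
- Two-sided normal approximation: n = (1 + 1/1.111) × (2.393 + 0.842)² × 2.5² / 3.4² = 10.75, rounded up to 11, and again 12.2, rounded up to 13.

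The plan's 11/11/13 is reproduced. With 10% attrition, 35/0.9 = 38.9, consistent with the stated figure of about 40. The calculation is entirely about efficacy, so it does not support a safety-primary objective. It divides alpha over dose contrasts, so it does not match a single 16,000 µg primary contrast either.

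**Step 3. Illustration of one remedy.** Suppose 16,000 µg v placebo is the first test in a fixed sequence. Power is P(T > t at 1 − alpha), where T is noncentral t with noncentrality 3.4 / [2.5 × √(1/n1 + 1/n2)] and n1 + n2 − 2 degrees of freedom, one-sided.

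- 11 v 13: noncentrality 3.4/1.024 = 3.320, 22 df.
- 10 v 12 (0.9 × 11 = 9.9 and 0.9 × 13 = 11.7, rounded): noncentrality 3.4/1.070 = 3.176, 20 df.

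| One-sided alpha | 11 v 13 | 10 v 12 |
|---|---|---|
| 0.05 (first in sequence) | 94.2% | 92.2% |
| 0.0167 (one of three) | 84.6% | 80.7% |
| 0.0125 (one of the four the SAP lists) | 81.2% | 76.8% |

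**The case against.** Much of the plan points in one direction. The synopsis and SAP agree on the primary measures. Both sample-size sections use the same efficacy difference. SAP 9.3 analyses 16,000 µg v placebo first and treats the other contrasts as repeats. Safety has no success threshold, so a safety-primary reading offers no rival test to win on. All of this stands, and it limits the point to the ranked objectives and the alpha plan.

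A reader might infer that the trial has no primary question at all and that success could be declared under whichever version suits the data. The documents do not support that. The measures are agreed between synopsis and SAP, and any risk of selecting among measures, visits and contrasts is a separate multiplicity issue. A reader might also infer that the SAP drops efficacy of 8,000 µg; only its ranked objectives omit it. Nor are there three rival primary objectives: the synopsis ranks outcomes, not objectives.

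It could be said that the SAP may refine the protocol. Protocol 10.3 allows the methods of that section to be updated before the code is broken. It does not extend to the objectives in Section 2.0.

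Finally, the SAP references two protocol versions, and it cannot be confirmed which one was supplied. Part of the gap between protocol and SAP could come from that. The mismatch between Protocol 2.0 and the synopsis's own primary outcomes does not depend on it.

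**Conclusion.** The concern holds as a contradiction between ranked objectives. It rests on intact sentences in Protocol 2.0 and SAP Section 4, and the alpha plan agrees with neither ranking. The synopsis sides with the SAP on primary measures and against Protocol 2.0. The statement that safety is the synopsis's secondary outcome is not needed for this conclusion.

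The inconsistency has no effect size. A reader might take the gap of about 10 to 12 percentage points in power (94% v 85%, or 92% v 81%) as the harm it does. It is the gain from one possible redesign, and it assumes the plan's own difference of 3.4 and SD of 2.5, one-sided testing and an exact t-test. It should be corrected before unblinding, because afterwards the choice of primary contrast could no longer be shown to be independent of the results.

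**What to change.** Before the code is broken, reconcile Protocol 2.0, the synopsis and SAP Section 4 to one ranked primary objective and one primary contrast. Which ranking to keep is the sponsor's decision. Then make the alpha plan in Protocol 10.3.2 and SAP Section 8 match it, with the same list and count of contrasts in both.

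- If safety is kept as primary, say that it is assessed descriptively and that the sample size supports the secondary efficacy comparisons.
- If 16,000 µg v placebo is kept as the primary efficacy contrast, one option is to test it first at one-sided 0.05, then 8,000 µg v placebo at the same level only if the first succeeds. Dose v dose and pooled active v placebo go later in the sequence or are labelled exploratory.
- If both doses are to count equally, put efficacy of 8,000 µg into the SAP's ranked objectives and keep the alpha split, corrected for the number of contrasts actually listed.

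The cost is more than wording. It is a protocol amendment, which Protocol 12.2.2 expects to be submitted to the IRB and FDA, plus a revised SAP. No new data or participants are needed.
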